## 7.2. Exclusion Criteria

The presence of any of the following at entry, will exclude a subject from study enrolment:

- Less than 37 weeks gestational age at birth
- Known blood group incompatibilities which can result in hemolytic disease of the newborn (e.g., Rh-negative mother, presence of antibodies on neonatal red blood cells, etc.)
- Total bilirubin values approaching an exchange transfusion as defined by local guidelines (Section 18.2)
- Haemoglobin value of <13.0 g/dL
- Platelet count of less than 50,000 cells/mm^3)
- Decreased total white blood cell count (Grade 3 and above)
- Creatinine value more than 1.3 the upper limit of normal (ULN) for gestational age and postnatal age (Grade 2 and above)
- AST or ALT of more than 2.5 the ULN (Grade 2 and above)
- Any other current Grade  $\geq 3$  event on the DAIDS toxicity table
- Severe congenital abnormalities or critically ill neonates at discretion of the examining clinician
- Receiving medicine(s) that can impact DTG pharmacokinetics (Section 8.7)
- Participation in another clinical trial
- HIV-infected neonates

## 8. Study Treatment

The study treatment is a 10 mg scored dispersible tablet of DTG for oral suspension, supplied by Mylan (Viatris) Ltd.

To administer 5 mg of a DTG dose, the 10 mg DTG-DT will be broken in half along the score and one half of the tablet (5 mg) will be dispersed in 5 mL of water. The entire volume will then be administered to the neonate. Partial volumes of the oral suspension are not allowed as the drug does not disperse evenly.

## 8.1. General Pharmacokinetics of Dolutegravir

DTG is rapidly absorbed following oral administration with maximum plasma concentrations ( $C_{max}$ ) 2 to 3 hours post-dose. DTG is primarily metabolized via UDP-glucuronosyltransferases (UGT)-1A1 with some contribution from cytochrome (CYP)-3A and these metabolites are excreted in the urine. Renal elimination of unchanged DTG is <1% of the dose. Small, reversible increases in serum creatinine with DTG use have been shown due to inhibition of tubular secretion of creatinine (via inhibition of OCT2), but without affecting renal glomerular function (27).

The terminal plasma half-life of DTG after oral intake is approximately 14 hours. Steady-state DTG pharmacokinetics are achieved within ~5 days with once daily oral dosing and average accumulation ratios for AUC,  $C_{max}$ , and  $C_{24}$  range from 1.2 to 1.5 in adults. A summary of the steady-state PK parameters for DTG in adults with HIV receiving 50 mg once and twice daily are shown in **Table 1** (19).

**Table 1.** Geometric Mean (%CV) Steady-State PK Parameters of DTG in Adults Living with HIV

PK Parameters	50 mg Once Daily	50 mg Twice Daily
AUC 0-24 (µg·h/mL)	53.6 (27)	75.1 (35)
$C_{max}$ (µg/mL)	3.67 (20)	4.15 (29)
$C_{min}$ (µg/mL)	1.11 (46)	2.12 (47)

Dolutegravir is >98% bound to human plasma proteins. A population PK analysis estimated the apparent volume of distribution (V/F) and apparent clearance (CL/F) following 50 mg once daily to be 17.4 Litres (L) and 1.0 L/hour, respectively. DTG concentrations have also been detected in the cerebrospinal fluid indicating it crosses the blood–brain barrier. Of note, DTG plasma concentrations increase in a less than dose-proportional manner at doses over 50 mg.

Both film-coated and dispersible tablets of DTG can be taken with or without regard to food; however, intake of DTG with food increases its absorption and slows the rate of absorption. For example, with a high fat meal the DTG AUC0-inf and  $C_{max}$  increase by ~65% and the  $T_{max}$  increases from 2 to 5 hours. Dolutegravir has been shown to be a substrate of UGT1A3, UGT1A9, BCRP, and P-glycoprotein *in-vitro*, so concomitant medications that induce or inhibit these enzymes and/or transporters may impact the pharmacokinetic profile of DTG.

Multiple drug-drug interactions have been reported and, in some cases, DTG dose adjustment from once to twice daily is necessary (e.g., carbamazepine, rifampicin), or changes to the timing of DTG administration relative to concomitant drugs (e.g., medications containing polyvalent cations, oral iron and/or calcium supplements) is needed. Refer to Section 8.7 – Concomitant Medications for more information.

## 8.2. Dolutegravir Dosing in Paediatrics

Several formulations of DTG have been approved by the US FDA for use in children: 10, 25 and 50 mg FCT for oral use and a 5 mg DT for oral suspension. The pharmacokinetics of these formulations of DTG have been evaluated in the IMPAACT P1093 trial [ClinicalTrials.gov Identifier: NCT01302847] and in 2 weight-band-based PK substudies from the ODYSSEY trial [NCT02259127, (28, 29)]. Of note, the bioavailability of the DTG-DT is ~1.6-fold that of DTG-FCT (19). Steady-state plasma PK of DTG at doses by weight bands are summarized in **Table 2**.

**Table 2.** Summary of DTG PK Parameters in children living with HIV (analyses from IMPAACT P1093 and ODYSSEY trials (19))

Weight Band	DTG Dose	n	Pharmacokinetic Parameter Geometric Mean (%CV)		
			C max (µg/mL)	AUC 0-24 (µg·h/mL)	C 24 (µg/mL)
3 kg to <6 kg	5 mg DT OD	8	3.80 (34)	49.37 (49)	0.962 (98)
6 kg to <10 kg	15 mg DT OD	17	5.27 (50)	57.17 (76)	0.706 (177)
10 kg to <14 kg	20 mg DT OD	13	5.99 (33)	68.75 (48)	0.977 (100)
14 kg to <20 kg	25 mg DT OD	19	5.97 (42)	58.97 (44)	0.725 (75)
20 kg to <25 kg	30 mg DT OD	9	7.16 (26)	71.53 (26)	0.759 (73)
≥20 kg	50 mg FCT OD	49	4.92 (40)	54.98 (43)	0.778 (62)

DT: Dispersible tablet; FTC: Film-coated tablet; OD: Once daily

Mean steady-state DTG exposures (AUC0-24h) and C24h in paediatric participants with HIV were comparable to those in adults receiving 50 mg once or twice daily. Mean DTG Cmax was generally higher with once daily dosing in children than adults (Table 1), but the increase was not considered clinically significant as the safety profiles were similar in both populations.

The paediatric DTG dosing recommendations were derived from a population PK analysis combining IMPAACT P1093 and ODYSSEY data (20). The US FDA licensed weight-band dosing of the DTG-DT is now recommended for infants and children in the WHO dosing guidelines (9). Table 3 shows the 2021 WHO weight-based dosage of the scored 10 mg DTG-DT for infants and children 4 weeks and older and weighing at least 3 kg.

**Table 3:** 2021 WHO weight-band dosing for DTG 10 mg scored dispersible tablet in infants 4 weeks and older & weighing at least 3 kg

Weight Band	Dolutegravir Tablets for Oral Suspension	
	Daily DTG Dose	Number of 10-mg Tablets
3 kg to <6 kg	5 mg OD	½ (one-half)
6 kg to <10 kg	15 mg OD	1 ½ (one and one-half)
10 kg to <14 kg	20 mg OD	2 (two)
14 kg to <20 kg	25 mg OD	2 ½ (two and one-half)
20 kg or greater	30 mg OD	3 (three)

OD: Once daily

The weight-based DTG dose is recommended to be increased for children receiving rifampicin-containing TB treatment to twice daily.

### 8.2.1. Dolutegravir Dosing in Neonates

**No specific DTG dosing guidelines are available for neonates.** Based on the WHO weight band dosing guidelines the DTG dose range is between 0.85 to 1.67 mg/kg for children >4 weeks and weighing between 3 and 5.9 kg. In Cohort 1A, 5 mg of DTG, i.e., half of the scored 10 mg DTG-DT, will be administered to neonates who are ≥14 days and <28 days of life. For a 3 kg neonate, this translates to a 1.67 mg/kg dose, but higher drug exposures are anticipated due to the expected slower metabolism in these younger infants. If the drug exposures following

this single dose are found to be safe, it is planned to administer a single 5 mg dose of DTG to neonates  $\leq 14$  days (Cohort 1B).

It is unknown the extent to which the DTG exposure will be increased as the enzyme pathways involved in DTG metabolism (UGT1A1 and CYP3A) mature at different rates during early life (30, 31). As expected, the washout elimination of DTG in neonates after *in utero* exposure was slow, with a median elimination half-life of 32.8 hours compared to 12-14 hours in children and adults. In this context, physiologically based pharmacokinetic (PBPK) modelling (32) has been utilized to predict DTG PK and dose optimization in neonates (33). This PBPK model combined existing knowledge on the anatomical, physiological, and metabolic changes (i.e., ontogeny of CYP3A4 and UGT1A1) in neonates with available physicochemical and *in-vitro* data of DTG. This PBPK model was validated using observed clinical data for RAL and midazolam in neonates. Using the final PBPK model, multiple DTG dose strategies were simulated in 100 healthy term virtual neonates (weight ranging from 3.0 to 4.5 kg) with the goal of achieving therapeutic DTG plasma  $AUC_{0-24}$  (50.1  $\mu\text{g}\cdot\text{h}/\text{mL}$ ) and trough concentration (0.99  $\mu\text{g}/\text{mL}$ ) observed in children. **The model predictions indicated that a 5 mg DTG dose may be suitable for term neonates, but any regimen would likely require increased dosing intervals during early life compared to older infants (e.g., every 48 or 72 hours compared to every 24 hours).** The authors' preferred regimen was 5 mg DTG doses every 48 hours from Day 1–20 of life, increasing to 5 mg once daily on Day 21. An important caveat of this PBPK model was the absence of maternal transfer of DTG through the placenta or breast milk. It has been shown that DTG readily crosses the placenta with a reported cord blood to maternal plasma ratio of 1.25 (1.07–1.40) (34). Breastfeeding has been reported to contribute relatively little to infant plasma exposure in the DolPHIN-1 study. The relative infant dose to that of the mother was estimated to be 0.27% (range, 0.13%–0.71%;  $n = 26$ ) (35).

The 2021 WHO guidelines recommend ART to be initiated urgently among all pregnant and breastfeeding women living with HIV and the preferred 1st-line regimen is DTG in combination with an NRTI backbone (9). Most high burden countries have adopted DTG in their national guidelines, including South Africa. The introduction of the generic FDC of TDF/3TC/DTG or "TLD" across Africa is facilitating the rapid transition of adults to DTG, with the majority of adults now receiving DTG based-ART in many countries (36). The South African National Department of Health supports the guidance that all newly diagnosed pregnant women should be initiated on TLD (26). For this reason, it was decided to focus on HIV-exposed neonates born to mothers on DTG-based regimens, so the PETITE-DTG study results are applicable to South Africa and similar settings. Thus, it is important to consider transplacental transfer of DTG and any potential impact it may have on neonatal DTG dosing and exposure.

A recent population PK modelling and simulation study using data from the IMPAACT P1026s trial was performed to assess DTG dosing requirements during the first days of life as a function of maternal DTG dosing history (37). Maternal and infant population PK models were developed to describe infant DTG concentrations at delivery (i.e., estimate the *in-utero* dose of DTG) and transplacental washout. Of note, the neonate PK model incorporated a maturation function for UGT1A1-mediated DTG clearance, and the  $K_a$  was fixed to the adult value. Using these PK models, Monte Carlo simulations of virtual infants were performed to simulate neonatal concentrations following two doses of DTG after birth for infants born to mothers receiving DTG prior to delivery. The lower and upper ranges of the PK targets selected was 0.256  $\mu\text{g}/\text{mL}$  ( $4\times IC_{90}$ ) and 7.34  $\mu\text{g}/\text{mL}$  (2-fold above the adult  $C_{\text{max}}$  value), respectively.

Simulations revealed that among neonates whose mother had taken DTG between 6 hours to 24 hours prior to delivery, a 5 mg DTG dose at 24 to 72 hours after birth maintained median  $C_{max}$  concentrations below the target. These data are also supportive that a single 5 mg DTG dose at >3 days of life proposed in Stage 1 of the PETITE-DTG study will not lead to excess DTG concentrations. **However, it is clear that the timing of the second DTG dose is very important.** For example, if the first dose was administered 48 hours after birth, and a second dose 48 hours later, median  $C_{max}$  were within the target; but administering the second dose 24 hours after the first dose led to a  $C_{max}$  above the target. The optimal DTG dosing strategy for neonates remains to be determined and the data generated in Stage 1 of the PETITE-DTG study will guide the timing of DTG doses for the multi-dose stage in Cohort 2.

Another consideration is the background NVP ARV infant prophylaxis. Nevirapine is an inducer of CYP3A which is one of the metabolic pathways of DTG and therefore concomitant use could impact DTG concentrations. Indeed, a drug-drug interaction study of DTG and NVP in adults revealed that DTG  $C_{max}$ ,  $AUC_{0-24}$ ,  $C_{24}$  were reduced by an average of 8%, 19% and 34%, respectively (38). The oral clearance of DTG was 23% faster with concomitant NVP use (1.12 L/r vs 0.91 L/hr), with the plasma half-life 15% faster. Maximum induction of CYP3A by NVP occurs 2 to 4 weeks after initiation (39, 40). Based on this data it is anticipated that concomitant NVP use could decrease DTG concentrations in neonates. As the future clinical application of DTG in neonates will be without concomitant NVP, determining optimal DTG dosing in neonates in the absence of NVP will provide the most informative data. For this reason, neonates who receive multiple doses of DTG in Stage 2 of the PETITE-DTG study will receive ZDV prophylaxis, instead of NVP, for the duration of the study. Only infants born to virologically suppressed mothers will be enrolled in Stage 2.

Overall, these data are encouraging and support the assessment of the 5 mg DTG-DT in neonates; however, to be cautious, a multi-step, two-stage study design was selected for the PETITE-DTG trial to maximise the safety of study participants. Only if no safety concerns are observed in Stage 1, and an appropriate DTG dosing regimen is identified, will the study proceed to assess multi-doses of the DTG-DT in Stage 2.

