### 6.1.1. Stage 1: Single Dose of the DTG generic dispersible tablet

Cohort 1A will open to accrual first (Schema, Section 6.2, **Figure 1**).

- **Cohort 1A:** 8 neonates weighing  $\geq 2000$  g at birth will receive a single dose of 5 mg DTG at  $\geq 14$  days and  $< 28$  days of life.

DTG will be administered in addition to standard of care ARV prophylaxis. After Cohort 1A is complete, and if no safety concerns are noted, accrual will continue into Cohort 1B. However, if safety hold criteria are met in Cohort 1A (Section 11.1.1), the study will be paused and data reviewed by the DSMB.

- **Cohort 1B:** 8 neonates weighing  $\geq 2000$  g at birth will receive a single dose of 5 mg of DTG at  $< 14$  days of life.

If safety hold criteria are met during Cohort 1B (Section 11.1.2), the study will be paused and data reviewed by the DSMB. After Cohort 1B is complete, all safety and PK data for **Stage 1** will be reviewed. Pharmacokinetic modelling and simulation analyses using Stage 1 PK data will be performed to select the multi-dose schedule of the DTG dispersible tablet for Cohort 2 (Section 11.4). All findings will be presented to the DSMB and agreed upon before opening Cohort 2.

[figure not shown]

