### 9.2.1.1. Cohort 1A: PK Visit 1a/1b

After study entry, PK Visit 1a and 1b for the neonate will be scheduled at **≥14 days and <28 days of life**. On the morning of the PK visit 1a, study nurses and physicians will take a medical history and examine the neonate. Afterwards, a single 5 mg dose of DTG (half of the 10 mg DTG-DT) will be administered. The study team will support the preparation and administration of the DTG-DT mixed with water with the parent(s) or caregiver/legal guardian and document the exact time of intake used for administration. Acceptability testing of the DTG-DT will be performed.

Following an observed dose, blood will be drawn at 1, 2, 3, 4, 6 (PK Visit 1a) and 24-30-hours (PK Visit 1b) post-dose. A blood draw window of +/- 15 minutes is acceptable for samples up to 6 hours post-dose. The last samples can be drawn anytime between 24 and 30-hours post-dose. It is planned to draw 0.4 mL per time point - a total blood volume of 2.4 mL for PK assessment. A short intravenous catheter (heparin lock) can be used to reduce repeated skin puncture and ease the discomfort of blood sampling.

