### 9.2.1.2. Cohort 1A: Safety Visits

One week after PK visit 1a (+/-4 days), we will conduct a clinical and laboratory safety visit. Medical staff will take a recent medical history from the parent(s) or caregiver/legal guardian and examine the neonate. Study required bloods will be drawn, and an HIV NAT will be performed. If any tests yield abnormal results, as specified by protocol specific safety criteria (Section 10), we will consult paediatricians for appropriate management of the neonate. If the clinical examination and all tests are normal, a telephonic safety visit will be conducted 2 weeks after PK Visit 1a (+/-4 days). Medical staff will once again take a recent medical history from the parent(s). If no issues are reported, the neonate will exit the study at the conclusion of this visit. If any concerns are noted, the neonate will be brought back for clinical and special investigations as needed. The total study duration for each individual will depend on the age at enrolment and can range from 2 to 6 weeks.

If study safety hold criteria (Section 11.1.1) are met at any time during Cohort 1A the study will be paused, safety data reviewed, and a DSMB meeting held to determine if the study should continue (Section 6.2, **Figure 1**). After Cohort 1A is complete, if no major safety concerns are noted, accrual will continue into Cohort 1B.

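### Section 8.2.1 makes the Cohort 1B dose depend on Cohort 1A drug exposures being safe, but the operative rules open 1B on clinical safety alone

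*Protocol*

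**What the plan says.** Section 8.2.1 explains the 5 mg dose in Cohort 1A and says: "higher drug exposures are anticipated due to the expected slower metabolism in these younger infants. If the drug exposures following" and then "this single dose are found to be safe, it is planned to administer a single 5 mg dose of DTG to neonates" in the younger age group. The term for exposure appears twice in adjacent sentences, and the first use is plainly pharmacokinetic because it is tied to slower metabolism.

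The rules for moving on are worded differently. Section 6.1.1 (and the synopsis) has: "After Cohort 1A is complete, and if no safety concerns are noted, accrual will continue into Cohort 1B". Section 9.2.1.2 has: "After Cohort 1A is complete, if no major safety concerns are noted, accrual will continue into Cohort 1B". The Cohort 1A hold criteria in 11.1.1 count related adverse events and contain no concentration criterion.

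PK review appears elsewhere. Sections 6.1.1 and 9.2.2.2 place the review of all Stage 1 PK data after Cohort 1B. Section 11.4 gives its purpose as choosing the Cohort 2 schedule. Section 12.2.1 plans an interim after Cohort 1A, described as a futility analysis on safety data, PK data or both. The only upper exposure limit, a Cmax of 17.0 µg/mL (11.4.1), is applied to regimen selection for Cohort 2 and to the Cohort 2 interim (11.5).

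**The concern.** A reader of 8.2.1, including an ethics or regulatory reviewer, would credit the trial with an exposure check before the youngest infants are dosed. No operative rule in the text carries it out.

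The hazard that the protocol names depends on concentration: displacement of bilirubin from albumin at high dolutegravir levels (10.7.2, 11.4.1). Section 4.4 puts older infants first because the dose is fixed and metabolism is expected to be slower in early life. The 1A concentrations are the data that speak most directly to that reason, and the rules do not require anyone to look at them before 1B opens.

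**Working it through.** **1. The provisions side by side**

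| Section | Rule | 1A concentrations required before 1B? |
|---|---|---|
| 8.2.1 | 1B dose planned if 1A exposures are found safe | Yes, read literally |
| Synopsis, 6.1.1 | 1A complete, no safety concerns | No |
| 9.2.1.2 | 1A complete, no major safety concerns | No |
| 11.1.1 | Hold on related adverse events | No |
| 6.1.1, 9.2.2.2, 11.4 | PK review after 1B, to choose the Cohort 2 schedule | No |
| 12.2.1 | Interim after 1A on safety, PK or both; not linked to opening 1B | Optional |
| 14.3 | Minimum DSMB meetings: before Cohort 2, halfway through it, or on a hold | No |

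**2. Can the adverse-event gate stand in for an exposure check?** For a related Grade 3 or higher event with true rate p, the chance that at least 2 of 8 infants have it is 1 − (1−p)^8 − 8p(1−p)^7. As a check on the method, the chance of at least one event at p = 5% is 1 − 0.95^8 = 0.337, matching the 0.34 in Table 10. For at least two, the results are 0.057 at p = 5%, 0.187 at 10% and 0.497 at 20%. Eight infants without a hold therefore say little about exposure.

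For bilirubin specifically, Table 9 grades phototherapy as Grade 2 and exchange transfusion as Grade 3. A hold for hyperbilirubinaemia alone thus needs two related exchange transfusions or one related life-threatening or fatal case. The chemistry panel in Table 6 is total and direct bilirubin; free bilirubin is not listed.

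**3. Timing of the bilirubin sample.** Section 9.2.1.2 says: "One week after PK visit 1a (+/-4 days), we will conduct a clinical and laboratory safety visit". That is day 7 ± 4, so day 3 to day 11, and it is the only scheduled post-dose bilirubin in 1A. With simple exponential decline, the fraction left is 2^(−t/half-life). Assume a half-life between 14 h (adult value, 8.1) and 32.8 h (neonatal washout, 8.2.1):

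- Day 3 (72 h): 2.8% to 21.8% remains.
- Day 7 (168 h): 0.02% to 2.9% remains.

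The sample is therefore taken well after the peak.

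**4. How a 17.0 µg/mL trigger would behave.** Take Cmax as log-normal with σ = √ln(1+CV²). The starting geometric mean is 3.80 µg/mL, CV 34% (Table 2, 3 to <6 kg). A CV of 50% is borrowed from the CL/F planning value in 12.1. Each infant exceeds the limit with probability q = 1 − Φ[ln(17.0/GM)/σ], and any of 8 does so with probability 1 − (1−q)^8.

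| Geometric mean, µg/mL | CV 34% | CV 50% |
|---|---|---|
| 3.80 (Table 2) | <0.01% | 0.6% |
| 7.6 (doubled, assumption) | 5.8% | 30% |
| 11.4 (tripled, assumption) | 62% | 83% |

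The trigger is quiet at ordinary exposures and fires mainly if exposure is about twice Table 2 or more. A limit of 7.34 µg/mL (the simulation target in 8.2.1) would be too sensitive: at 3.80 and CV 34%, 2.3% per infant and 17% for any of 8. Table 2 values are at steady state, so single-dose peaks should be no higher for the same clearance.

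**5. Samples and waiting time.** Six samples × 8 infants = 48, and "The last samples can be drawn anytime between 24 and 30-hours post-dose". The closing phone call is at day 14 ± 4. For the last infant, the time between the last sample and the end of follow-up runs from day 10 − 30 h = 8.75 days to day 18 − 24 h = 17 days.

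**The case against.** The best defence is that 8.2.1 is dosing rationale, states only a plan, and can be read as meaning that the dose was clinically tolerated. It gives no threshold, and 11.4.1 concedes that no clear toxicity cut-off exists for Cmax. The end of 8.2.1 also describes the move to Stage 2 in terms of safety concerns. That reading is possible, but it sits badly with the pharmacokinetic use of the same term one sentence earlier.

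A PK look before 1B is also not ruled out. The 12.2.1 interim may include it, the DSMB meetings listed are a minimum, the DSMB Charter is a separate document, and the schema in Figure 1 was not available to this review. The text citing Figure 1 mentions only safety holds. So PK review before 1B is optional in the text, not excluded.

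The mitigation is substantial and stands. Infants get one dose, older ones first. Bilirubin near exchange level and blood-group incompatibility are excluded, and 1B has its own hold criteria (11.1.2). Section 8.2.1 cites simulations in which 5 mg at 24 to 72 h of life kept median Cmax below the 7.34 µg/mL target, and concludes that "a single 5 mg DTG dose at >3 days of life proposed in Stage 1 of the PETITE-DTG study will not lead to excess" concentrations. A reader might infer that 1B lacks support for early dosing because 9.2.2.1 sets only an upper age. The documents do not bear that out, since the simulations cover dosing from 24 h.

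Slower elimination alone also moves a single-dose peak only modestly. With Tmax 2 to 3 h and a 12 h half-life, removing all elimination before the peak raises it by about 2^(2/12) − 1 = 12% to 2^(3/12) − 1 = 19%. That is a reason to look at the last concentration as well as Cmax. Finally, 1A data cannot show placental carry-over or the least mature metabolism seen in 1B.

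**Conclusion.** The inconsistency is real and moderate: 8.2.1 states an exposure condition for Cohort 1B that no rule in the visible text applies. The conclusion rests on reading exposure in 8.2.1 pharmacokinetically and on Figure 1 holding no PK step.

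A reader might go further and infer that 1B infants face unsafe concentrations, or that the two cohorts differ materially in exposure. The documents support neither. No harm is shown, the size of any difference is unknown, and the doubled and tripled means above are assumptions used only to describe the trigger. A wholly clinical gate between two single-dose cohorts could be defended, but 8.2.1 should not then describe something else. The point merits correction and does not call the design into question.

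**What to change.** - In 12.2.1, make the interim after Cohort 1A cover both safety and PK.
- In 6.1.1 and 9.2.1.2 (and the matching synopsis text), state that available 1A Cmax and last concentrations are reviewed before the first 1B dose, with referral to the DSMB if any 1A Cmax exceeds 17.0 µg/mL or a lower limit that the pharmacology team justifies.

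Rewording 8.2.1 to a clinical condition would remove the contradiction for the price of one sentence, but would change nothing the trial does. It is the fallback if no PK check is intended.

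No extra samples are needed. The cost is a possible delay before 1B while samples are shipped on dry ice to the laboratory in Chiang Mai (11.2.1), assayed and reviewed. The 9 to 17 days of remaining follow-up for the last 1A infant absorb only part of that, because the documents give no shipping or assay time. Sending earlier infants' samples in batches would shorten the wait.

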
Study design
	
Participants will be enrolled in two stages:
 
 
Stage 1 will assess a single dose of the DTG dispersible tablet in two sequential cohorts: Cohort 1A (n=8) and Cohort 1B (n=8).
 
Stage 2 will assess multiple-doses of the DTG dispersible tablet in a single cohort: Cohort 2 (n=24).
 
 
Per national guidelines, all infants receive a birth HIV nucleic acid test (NAT). HIV NAT test results for the infant may or may not be available (HIV pending) at the time of study entry. If an HIV NAT result comes back positive whilst the neonate is on study, the neonate will not receive any further DTG doses, revert to standard of care antiretroviral therapy (ART), and be followed for safety for the duration of the study.
 
Stage 1: Single Dose of the DTG dispersible tablet
 
Eligible HIV-exposed term neonates (pending HIV status) on standard of care ARV prophylaxis will be enrolled. Cohort 1A will open first.
 
 
Cohort 1A: 8 neonates weighing <math>\geq 2000</math> g at birth, born to women on DTG-based ART, will receive a single 5 mg dose of the DTG dispersible tablet at <math>\geq 14</math> days and <math>< 28</math> days of life. Following DTG administration, blood samples (0.4 mL/time point) will be drawn at 1, 2, 3, 4, 6, 24-30 hours post-dose. All neonates will be followed for safety until 2 weeks after the pharmacokinetic evaluation visit. DTG will be administered in addition to standard of care ARV prophylaxis.
 
 
After Cohort 1A is complete, and if no safety concerns are noted, accrual will continue into Cohort 1B. However, if safety hold criteria are met in Cohort 1A (Section 11.1.1), the study will be paused and data reviewed by the Data and Safety Monitoring Board (DSMB).
 
 
Cohort 1B: 8 neonates weighing <math>\geq 2000</math> g at birth, born to women on DTG-based ART, will receive a single 5 mg dose of the DTG dispersible tablet at <math>< 14</math> days of life. Following DTG administration, blood samples (0.4 mL/time point) will be drawn pre-dose, and at 1, 2, 4, 6, and 24-72 hours post-dose. All neonates will be followed for safety until 2 weeks after the PK visit. DTG will be administered in addition to standard of care ARV prophylaxis.
 

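### Cohort 1B has no stated minimum dosing age, although section 8.2.1 describes the Stage 1 dose as given after 3 days of life

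*Protocol*

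**What the plan says.** All references are to the protocol; the point concerns Cohort 1B only, because Cohort 1A has an explicit floor of 14 days.

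- **Rationale, section 8.2.1.** A population PK simulation that included maternal DTG found that, with mothers dosed 6 to 24 h before delivery, "a 5 mg DTG dose at 24 to 72 hours after birth maintained median" Cmax below its target of 7.34 µg/mL. The next sentence takes this as further support for "a single 5 mg DTG dose at >3 days of life proposed in Stage 1".
- **Same section, earlier.** If Cohort 1A exposures are safe, "it is planned to administer a single 5 mg dose of DTG to" neonates aged 14 days or less. No lower age is given.
- **Operative windows.** In the synopsis, Cohort 1B neonates "will receive a single 5 mg dose of the DTG dispersible tablet at" under 14 days of life. In section 6.1.1 they "will receive a single dose of 5 mg of DTG at" under 14 days. Section 9.2.2.1 and Table 7 repeat that upper limit for PK Visit 1a.
- **Entry.** Sections 7.1 and 9.2.2 require entry by day 3. That is an upper limit on entry, not a lower limit on dosing. The exclusion criteria in section 7.2 set no minimum age.
- **The other cited model.** The PBPK model's preferred regimen starts on Day 1, but section 8.2.1 adds: "An important caveat of this PBPK model was the absence of maternal transfer of DTG through the placenta or breast milk".

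**The concern.** An ethics committee or DSMB member who reads section 8.2.1 learns that the Stage 1 dose comes after 3 days of life. The site works from section 9.2.2.1 and Table 7, where a dose at 12 h would meet every written window and would not count as a deviation.

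The age matters because all Cohort 1B mothers take DTG and the newborn carries most of the maternal drug in the first day. Section 4.4 says there are no PK data on DTG in neonates, and section 11.4.1 says extremely high concentrations should be avoided because of bilirubin displacement. The Cohort 1B pre-dose sample measures carry-over, but nothing makes the dose depend on its result.

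**Working it through.** **1. Coverage of each dosing age**

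| Age at dose | Allowed by the Cohort 1B windows? | Agrees with the age in 8.2.1? | Within the simulation with maternal DTG? |
|---|---|---|---|
| Under 24 h | Yes | No | No |
| 24 to 72 h | Yes | No | Yes (median Cmax, mothers dosed 6 to 24 h before delivery) |
| After 3 days, under 14 days | Yes | Yes | Later than the simulated range, with less maternal drug left |

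The PBPK model does not fill the first row for this population, because it leaves out placental transfer.

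**2. Maternal drug remaining**

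Input: neonatal washout "with a median elimination half-life of 32.8 hours compared to" 12 to 14 h in children and adults (section 8.2.1). Fraction remaining at t hours = 0.5^(t/32.8):

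- 6 h: 0.881
- 12 h: 0.776
- 24 h: 0.602
- 48 h: 0.363
- 72 h: 0.218

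Relative to 24 h, carry-over is 0.881/0.602 = 1.46 times at 6 h and 0.776/0.602 = 1.29 times at 12 h.

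**3. Absolute size (assumption)**

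The protocol gives no neonatal concentration at birth. I assume the maternal level at delivery lies between the adult once-daily Cmin of 1.11 and Cmax of 3.67 µg/mL (Table 1), and apply the "cord blood to maternal plasma ratio of 1.25" with its reported range of 1.07 to 1.40 (section 8.2.1).

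- Level at birth: 1.11 × 1.07 = 1.19 to 3.67 × 1.40 = 5.14 µg/mL.
- Extra at 12 h compared with 24 h: 1.19 × 0.174 = 0.21 to 5.14 × 0.174 = 0.89 µg/mL.
- Extra at 6 h compared with 24 h: 1.19 × 0.279 = 0.33 to 5.14 × 0.279 = 1.43 µg/mL.
- Against the trial's 17.0 µg/mL limit (section 11.4.1): 0.21/17.0 = 1% to 0.89/17.0 = 5% at 12 h; 0.33/17.0 = 2% to 1.43/17.0 = 8% at 6 h.

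These rest on mean values and do not describe individual extremes.

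**4. What the stated duration implies**

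Duration = (dose day − entry day) + 14 days to the phone call. For Cohort 1A (entry days 0 to 13, dose days 14 to 27) this gives 15 to 41 days, in line with the 2 to 6 weeks in section 9.2.1.2. For Cohort 1B as written (entry days 0 to 3, dose days 0 to 13, dose not before entry) it gives 14 to 27 days, or 2 to 4 weeks. Section 9.2.2.2 states 3 to 4 weeks. A 21-day minimum needs dosing 21 − 14 = 7 days after entry, or 21 − 18 = 3 days if the call is made at the end of its +4-day window. The duration therefore points to later dosing, but it fixes no age.

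**The case against.** Several points on the other side stand.

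- **Section 8.2.1 does not carry Stage 1 safety alone.** It presents the simulation as additional support. The main protections are older neonates first, a single dose, bilirubin and blood-group exclusions, hold criteria, and DSMB review before multiple dosing. A reader might infer that the safety case collapses without the 3-day floor; the text does not support that.
- **Dosing before 24 h is unlikely.** It would need referral, consent, in-range haematology and chemistry before entry (Table 7, note a), and then a PK visit after entry. Creatinine eligibility depends on postnatal age, and the reference table in section 18.1 starts at 2 days. These are practical brakes, and standard-of-care results may be used, so none amounts to a minimum age.
- **The excess is small.** A reader might infer that early dosing would exceed 17.0 µg/mL. Nothing in the protocol shows that. The simulation's 7.34 µg/mL target is not this trial's limit.
- **A 24 h floor appears nowhere in the protocol.** The only age stated is more than 3 days. A reader might take 24 h as the intended limit, but it is only the lower edge of the cited simulation.
- **Figure 1 is not shown.** It may give dosing ages. A floor there would still leave the text inconsistent.
- **Cohort 2 also has no lower age for its first dose.** The carry-over argument applies there too, but section 8.2.1 states no conflicting age for that dose, and the Cohort 2 schedule is to be agreed with the DSMB after Stage 1.

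What remains is the conflict between the age in section 8.2.1 and windows that permit dosing from birth.

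**Conclusion.** The inconsistency is established from the text: section 8.2.1 gives an age of more than 3 days for the Stage 1 dose, and no Cohort 1B dosing window or eligibility criterion in the text enforces it. Dosing at 24 to 72 h contradicts that statement but is covered by the cited simulation. Only dosing before 24 h is outside both.

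The consequence is limited. The estimated extra carry-over depends on the assumed maternal level, the reported cord ratio and a single median half-life. It does not show that any infant would be dosed that early or would exceed the ceiling. I rate this a minor safety clarification, worth making because it concerns the age at which newborns are dosed and costs little.

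**What to change.** State one explicit lower limit for Cohort 1B dosing in the synopsis, section 6.1.1, section 9.2.2.1 and Table 7, and in Figure 1 if it gives dosing ages. Make the two sentences in section 8.2.1 agree with it. The limit should be one of:

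- **At least 24 h after birth and under 14 days**, which matches the lower edge of the simulation. Cost: one day of a 14-day scheduling window (days 0 to 13).
- **More than 3 days and under 14 days**, if the sponsor confirms that section 8.2.1 states the intent. Cost: about four of the 14 days (days 0 to 3), and the loss of single-dose data at the earliest ages at which Cohort 2, which enters infants under 7 days old, may begin multiple dosing.

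Either way the change is wording in six places, plus the figure if needed. Sample size, sampling times and analysis are unaffected.
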